### ***Secondary efficacy endpoints that measure binary responses***

Secondary efficacy endpoints that measure binary responses will be analyzed in the same fashion as the primary endpoint using primary statistical model.

### ***Continuous secondary efficacy endpoints***

The primary estimand for continuous secondary efficacy endpoints is defined in [Table 3](#) and will be analyzed using an analysis of covariance (ANCOVA) model with intervention group, documented history of atopy (atopic or non-atopic), stable use of TCS/TCI (yes or no), region (countries combined), baseline antidepressant use (yes or no), and relevant baseline measurement as covariate, with intercurrent event strategy and missing data handling as defined as in [Table 3](#). Specifically, data of participants taking the prohibited medications/procedures and/or rescue medications will be set to missing after the medication usage, and the worst postbaseline value on

or before the time of the medication usage will be used to impute missing endpoint value (for participants whose postbaseline values are all missing, the baseline will be used to impute). Participants who discontinue the treatment prematurely are encouraged to follow the planned clinical visits and in those participants who did not take the prohibited medications/procedures and/or rescue medications, all data collected after treatment discontinuation will be used in the analysis. For these participants, missing data may still happen despite all efforts have been tried to collect the data after treatment discontinuation. For participants who discontinue due to lack of efficacy, all data collected after discontinuation will be used in the analysis, and a WOCF approach will be used to impute missing data if needed. For participants who discontinued not due to lack of efficacy, a multiple imputation (MI) approach will be used to impute missing endpoint value, and this MI method will use all participants excluding participants who have taken the prohibited medications/procedures and/or rescue medications prior to timepoint of endpoint of interest and excluding participants who discontinue due to lack of efficacy.

Each of the imputed complete data will be analyzed by fitting an ANCOVA model as described above. The imputation number will be about 40. Statistical inference obtained from all imputed data will be combined using Rubin's rule. Descriptive statistics including number of participants, mean, standard error, and least squares (LS) mean changes (and standard error) will be provided. In addition, difference of the dupilumab group against placebo in LS means and the corresponding 95% confidence intervals (CI) will be provided along with the p-values.

See [Section 5.5](#) for the sample SAS code for the imputation and the analysis.

For the endpoint of percent change from baseline in WI-NRS at week 24, we will also perform an as-observed plus multiple imputation supplementary analysis as described below.

The data collected after taking all prohibited medications and/or rescue medications will be included in the supplementary analysis to evaluate the robustness of the primary analysis results with respect to the method of handling data while taking the prohibited medications (e.g. treatment policy strategy). In addition, for participants discontinuing the study treatment before Week 24, their off-study treatment values measured up to Week 24 will be included in the analysis. For participants having missing data at Week 24 regardless of reason(s), a multiple imputation (MI) approach will be used to impute the missing endpoint value.

## 4.5 TERTIARY/EXPLORATORY ENDPOINT(S) ANALYSIS

### 4.5.1 Definition of endpoint(s)

The exploratory endpoints are as follows:

- Use of high potency or superpotent TCS rescue medication through Week 24
- Use of systemic immunosuppressant through Week 24, constituting treatment failure
- Change from baseline in Hospital Anxiety and Depression Scale (HADS) total score to Week 24
- Change from baseline in EQ-5D-5L Single Index score to Week 24

- Change from baseline in EQ-5D visual analog scale (VAS) to Week 24
- Change from baseline in skin Pain-NRS to Week 4, Week 8, Week 12, and Week 24, respectively
- Change from baseline in Sleep-NRS to Week 4, Week 8, Week 12, and Week 24, respectively
- Missed school/work days through Week 24
- Incidence of skin-infection TEAEs (excluding herpetic infections) through Week 24
- Proportion of participants who achieve  $\geq 75\%$  healed lesions from PAS at Week 4, Week 8, Week 12, and Week 24, respectively
- Change from baseline in exact number of lesions in representative area (as determined from PAS) at Week 4, Week 8, Week 12, and Week 24, respectively
- Change from baseline in Participant Global Impression of Severity (PGIS) of PN to Week 4, Week 8, Week 12, and Week 24 respectively
- Proportion of participants with PGIS score of “none” at Week 4, Week 8, Week 12, and Week 24 respectively
- Proportion of participants with PGIS score of “none” or “mild” at Week 4, Week 8, Week 12, and Week 24 respectively
- Participant Global Impression of Change (PGIC) of PN at Week 4, Week 8, Week 12, and Week 24, respectively
- Proportion of participants with PGIC score of “very much better” at Week 4, Week 8, Week 12, and Week 24 respectively
- Proportion of participants with PGIC score of “very much better” or “moderately better” at Week 4, Week 8, Week 12, and Week 24 respectively

#### Hospital anxiety and depression scale (HADS)

The HADS is a PRO instrument for screening anxiety and depression in non-psychiatric populations; repeated administration also provides information about changes to a participant’s emotional state. The HADS consists of 14 items, 7 each for anxiety and depression symptoms; possible scores range from 0 to 21 for each subscale. The following cut-off scores are recommended for both subscales:

- 0 to 7: normal
- 8 to 10: borderline abnormal (borderline case)
- 11 to 21: abnormal

#### Euroqol 5 dimensions questionnaire (EQ-5D)

The Euroqol-5 dimensions (EQ-5D) is a standardized PRO measure of health status developed by the EuroQOL Group in order to provide a simple, generic measure of health for clinical and

economic appraisal. The EQ-5D consists of 2 parts: the descriptive system and the EQ visual analog scale (VAS). The EQ-5D descriptive system comprises the following 5 dimensions: mobility, self-care, usual activities, pain/discomfort, and anxiety/depression. Each dimension has 5 levels of perceived problems: “no problem”, “slight problems”, “moderate problems”, “severe problems” and “inability to do the activity”. The respondent is asked to indicate his/her health state by ticking (or placing a cross) in the box against the most appropriate statement in each of the 5 dimensions; this results in a 1-digit number expressing the level for that dimension. The digits for 5 dimensions can be combined in a 5-digit number describing the respondent’s health state. The EQ VAS records the respondent’s self-rated health on a vertical VAS where the endpoints are labeled “best imaginable health state (100)” and “worst imaginable health state (0)”. This information can be used as a quantitative measure of health outcome as judged by the individual respondents.

#### Skin Pain and sleep numeric rating scales (skin Pain-NRS, Sleep-NRS)

Participants will be asked to rate their worst skin pain in the past 24 hours using a 0 to 10 NRS, with 0 = No pain to 10 = Worst pain possible.

In addition, participants will be asked to rate their sleep quality on their past night upon awakening, using a 0 to 10 NRS, with 0 = Worst possible sleep and 10 = Best possible sleep.

Participants will complete the skin pain NRS and sleep quality NRS once a day.

#### Prurigo activity score (PAS)

The PAS is a clinician-reported outcome (ClinRO) measurement. The original PAS questionnaire Version 0.9 consists of 7 items, developed by expert clinicians in PN.

A 5-item simplified version of the PAS will be used in the current study. Item 4 (exact number of pruriginous lesions in representative area) and Item 5b (percentage of healed prurigo lesions in all pruriginous lesions) will be used for analyses. In addition, Item 2 (number of prurigo lesions) may be used for analysis too.

#### Participant Global Impression of Change of disease (PGIC) and Participant Global Impression of Severity (PGIS)

The PGIC is a one-item questionnaire that asks participants to provide the overall self-assessment of change in their PN overall on a 7-point scale, compared to just before participant started taking the study injection. Response choices are: 0 = “Very much better”, 1 = “Moderately better”, 2 = “A little better”, 3 = “No change”, 4 = “A little worse”, 5 = “Moderately worse”, 6 = “Very much worse”.

The PGIS is a one-item questionnaire that asks participants to provide the overall self-assessment of their disease severity on a 4-point scale for the past week. Response choices are: 1 = “none”, 2 = “Mild”, 3 = “Moderate”, 4 = “Severe”.

### Missed school/work days

Participants who are employed or enrolled in school will be asked to report the number of sick leave/missed school days since the last study assessment.

#### **4.5.2 Main analytical approach**

Exploratory efficacy endpoints will be analyzed using the same methodology as secondary efficacy for similar data (continuous or proportion) except the endpoints below.

- Use of high potency or superpotent TCS rescue medication through Week 24
- Use of systemic immunosuppressant through Week 24, constituting treatment failure
- Missed school/work days through Week 24
- Incidence of skin-infection TEAEs (excluding herpetic infections) through Week 24

The number of participants and percentage with the events for these endpoints will be provided in observed cases. In addition, the time (week) to first event for those participants will also be analyzed using Kaplan-Meier method and the duration of the rescue medication use may be summarized if applicable.

An additional exploratory endpoint of time to first select prohibited/rescue medication that impact efficacy will be provided. This includes medications where WOCF will be applied (see [Table 5](#)).

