
 
• To demonstrate a reduction in the use of rescue medication and systemic immunosuppressant
 
• To evaluate exploratory outcome measures
 
	
 
• Use of high potency or superpotent TCS rescue medication through Week 24
 
• Use of systemic immunosuppressants through Week 24, constituting treatment failure
 
• Change from baseline in Hospital Anxiety and Depression Scale (HADS) total score to Week 24.
 
• Change from baseline in EQ5D-5L to Week 24.
 
• Change from baseline in skin Pain numeric rating scale (NRS) to Week 4, Week 8, Week 12, and Week 24, respectively.
 
• Change from baseline in Sleep NRS to Week 4, Week 8, Week 12, and Week 24, respectively.
 
• Missed school/work days through Week 24.
 
• Incidence of skin-infection TEAEs (excluding herpetic infections) through Week 24.
 

 
• To evaluate the efficacy of dupilumab on skin lesions using a modified PAS 5-item questionnaire
 
• To evaluate the efficacy of dupilumab on other PN endpoints
 
	
 
• Proportion of participants who achieve <math>\geq 75\%</math> healed lesions from Prurigo Activity Score (PAS) at Week 4, Week 8, Week 12, and Week 24, respectively.
 
• Change from baseline in exact number of lesions in representative area (as determined from PAS) at Week 4, Week 8, Week 12, and Week 24, respectively.
 
• Change from baseline in Participant Global Impression of Severity (PGIS) of PN to Week 4, Week 8, Week 12, and Week 24, respectively.
 
• Participant Global Impression of Change (PGIC) of PN at Week 4, Week 8, Week 12, and Week 24, respectively.
 

PK	

 
• To evaluate pharmacokinetic (PK) and pharmacodynamic (PD) outcome measures
 
	
 
• Serum functional dupilumab concentrations and PK profile.
 
• Pharmacodynamic response for selected biomarkers (total IgE).
 

- a The early onset for significant change in the proportion of responders with WI-NRS reduction  $\geq 4$  between dupilumab and placebo will be claimed at Week xx if the p-value for Week xx is  $<0.05$  and the remaining timepoints also have nominal p-value  $\leq 0.05$  until Week 12.

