Dermatological preparations of high potency or superpotent TCS and TCI	No IMP discontinuation	Yes d (CDG b calcineurin inhibitors and corticosteroids narrow, Ticked 'RESCUE THERAPY' in CRF page)
a.	When yes, the estimand for the intercurrent event handling strategy will be as follows: hypothetical for continuous endpoints, and composite for responder and time-to-event endpoints. When no, a treatment policy strategy will be applied.	
b.	CDG=company drug groupings, CMQ=company MedDRA query, SDG= Standardized drug groupings.	
c.	Only if the antidepressant is initiated during the study or its dose is increased from baseline provided that medication was taken at least 3 months prior to screening.	
d.	As per medical adjudication, see Appendix 7 for details.	
e.	Only if the medication is initiated at Week 12 or Week 24, or the dose is increased from Week 11 to Week 12 or from Week 23 to Week 24.	

Blinded review of prohibited/rescue treatment (medication or procedure) based on [Table 5](#) and a pre-specified algorithm ([Appendix 7](#)) will be implemented before database locks by considering the type of medication or procedure, indication, timing, frequency and the potential impact of the use of the prohibited medications/procedures and rescue medications.

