### ***Prohibited medications/procedures***

The concomitant use of the following therapies is prohibited during the entire study. Study treatment will need to be discontinued in participants receiving these treatments:

- Systemic immunosuppressive/immunomodulating drugs (eg, systemic corticosteroids, cyclosporine, mycophenolate-mofetil, interferon gamma, Janus kinase inhibitors, azathioprine, methotrexate, hydroxychloroquine, dapsone, sulfasalazine, colchicine, etc)
- Other monoclonal antibodies (which are biological modifiers)
- Phototherapy, including tanning beds
- Naltrexone or other opioid antagonist
- Gabapentin, pregabalin, and thalidomide

The concomitant use of the following therapies is prohibited except if the dose has been stable for at least 3 months prior to screening, but study treatment will not need to be discontinued in participants receiving the treatments listed below. The dose should also remain stable (can be reduced or discontinued if medically indicated) and should not be increased during the study.

- Paroxetine, fluvoxamine, or other SSRIs
- SNRIs
- Amitriptyline or other tricyclic or tetracyclic antidepressants

The concomitant use of the following therapies is also prohibited during the entire study, but study treatment will not need to be discontinued in participants receiving the treatments listed below:

- Intralesional corticosteroid injections and cryotherapy

- Sedating antihistamine
- Non-sedating antihistamine if used specifically for the treatment of itch secondary to AD or PN

The number and percentage of participants who take the prohibited medications/procedures will be provided. In addition, the time (week) of first prohibited medication/procedure taken will also be analyzed using Kaplan-Meier method.

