### ***Rescue medications***

The following rescue medications may be used:

- Dermatological preparations of high potency or superpotent TCS and TCI.

If medically necessary (i.e., to control intolerable PN symptoms), rescue treatment for PN may be provided to study participants at the discretion of the Investigator.

Although the use of rescue medications is allowed at any time during the study, the use of rescue medications should be delayed, if possible, for at least 14 days following the initiation of the investigational treatment. The date and time of rescue medication administration as well as the name and dosage regimen of the rescue medication must be recorded in the eCRF.

- For the purpose of the efficacy responder analysis, a pre-specified algorithm will be used to classify rescue. In addition, a blinded review of all post-baseline medications to adjudicate rescue treatment, based on medical judgment, will be performed to adjudicate rescue. Participants who receive rescue treatment as per this adjudication during the study will be considered treatment failures.

The rescue medications will be analyzed by the same method as that used for prohibited medications/procedures.

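### The exploratory rescue endpoint counts topical corticosteroids only although rescue is defined as TCS and TCI, and its Kaplan-Meier analysis is loosely specified and has no between-arm estimate

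*SAP*

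**What the plan says.** **Objective and endpoint.** Protocol Table 1 and SAP Table 2 list the exploratory objective "To demonstrate a reduction in the use of rescue medication and systemic immunosuppressant". The rescue endpoint under it is "Use of high potency or superpotent TCS rescue medication through Week 24", repeated in SAP 4.5.1 and 4.5.2.

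**Rescue definition.** Protocol 6.5.1, SAP Table 5 and SAP Appendix 3 all define rescue as "Dermatological preparations of high potency or superpotent TCS and TCI". Table 5 selects it by "calcineurin inhibitors and corticosteroids narrow, Ticked 'RESCUE THERAPY' in CRF page", subject to blinded medical adjudication (footnote d and Appendix 7).

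**Analysis in SAP 4.5.2.** This endpoint is taken out of the secondary-endpoint methods. It gets a count and percentage in observed cases, and then "the time (week) to first event for those participants will also be analyzed using Kaplan-Meier method". The section also adds a separate endpoint, time to first prohibited or rescue medication, defined through Table 5.

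**Analysis in SAP Appendix 3.** "The rescue medications will be analyzed by the same method as that used for prohibited medications/procedures"; that method is a count and percentage, and "the time (week) of first prohibited medication/procedure taken will also be analyzed using Kaplan-Meier method". No end of follow-up is given. The same text begins "Although the use of rescue medications is allowed at any time during the study".

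**The concern.** Three features weaken the analysis for its stated purpose.

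- **Drug list.** A participant adjudicated as rescued with TCI alone is set to non-responder under Table 5 but counts as having had no rescue in the endpoint about rescue. No reason for the narrower list is given.
- **Risk set and censoring.** The antecedent of the phrase in 4.5.2 is the participants with the events just counted. A Kaplan-Meier curve on that group ends at 100% in each arm whatever the drug does. If all participants were meant, there is still no censoring rule, and observed cases does not say where event-free early leavers go in the denominator.
- **No comparison.** The objective is to demonstrate a reduction, yet no difference, ratio, confidence interval or test is planned.

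Rescue is also a failure component of the primary and key secondary estimands. Readers will look to this table to learn how much rescue each arm needed.

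**Working it through.** **Inputs from the documents.** 75 participants per arm and 15% dropout over 12 weeks (SAP section 2); last dose at Week 22 (Protocol 1.3); concomitant-medication window of last dose + 98 days (SAP Appendix 3); end of the Week 24 window at Day 172 (SAP Table 10 and 4.4.2). The plan gives no rescue rate, so there is no figure to reproduce.

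**Assumptions.** Week 24 rescue of 30% on placebo and 15% on dupilumab, with constant hazard λ = −ln(1 − p)/24 per week. This gives λ = 0.01486 and 0.00677.

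**1. Drug list.** If a share s of rescued participants use TCI only, the endpoint shows p(1 − s).

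| s | Placebo | Dupilumab | Difference (points) |
|---|---|---|---|
| 0% | 30% | 15% | 15 |
| 10% | 27% | 13.5% | 13.5 |
| 20% | 24% | 12% | 12 |
| 40% | 18% | 9% | 9 |

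With the same share in both arms the ratio stays at 0.5 and only the absolute difference shrinks. With unequal shares the ratio moves too: 30% TCI only on placebo and 10% on dupilumab gives 21% versus 13.5%, a ratio of 0.64.

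**2. Risk set.** With all participants at risk, cumulative incidence at Week 24 is 30% versus 15%. With only participants who had an event, it is 100% versus 100%. The median time among them is −ln(1 − p/2)/λ:

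- placebo: −ln(0.85)/0.01486 = 10.9 weeks
- dupilumab: −ln(0.925)/0.00677 = 11.5 weeks

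A halving of rescue would appear as a gap of about half a week. Rates of 40% versus 20% give 10.5 versus 11.3 weeks.

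**3. Observed-cases percentage.** Extend the 15% dropout at a constant rate to Week 24: μ = −ln(0.85)/12 = 0.01354 per week. The probability of an observed event is E = λ/(λ + μ) × [1 − e^(−24(λ+μ))], and of completing event-free F = e^(−24(λ+μ)).

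- Placebo: E = 0.259, F = 0.506
- Dupilumab: E = 0.129, F = 0.614
- Early leavers counted as event-free (E): 26% versus 13%
- Early leavers excluded, E/(E + F): 34% versus 17%

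The same data give either pair, depending on a rule the SAP does not state. The dropout figure is a sample-size allowance. Participants who stop treatment are asked to stay in the study, so real study exit may be lower and the gap smaller.

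**4. Follow-up end in Appendix 3.** If the rescue summary used the concomitant-medication window, a completer would be followed to Week 22 + 98/7 = Week 36. At constant hazard, 1 − (1 − p)^(36/24) gives 41% versus 22% in place of 30% versus 15%.

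**5. What a comparison could deliver.** At 30% versus 15%, SE = √(0.30 × 0.70/75 + 0.15 × 0.85/75) = 0.067, so the 95% CI is about 15 ± 13 points. Exact Fisher power at two-sided 0.05 is 0.53. Across the other assumed pairs it ranges from 0.32 (20% versus 10%) to 0.92 (40% versus 15%).

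**The case against.** The strongest reply is that this is a descriptive exploratory endpoint outside both testing hierarchies in SAP 4.6, and that a reader could still see a reduction. That stands. A reader might infer that the plan cannot show less rescue at all. The documents do not support this, because the count and percentage through Week 24 do not depend on the Kaplan-Meier wording, and every percentage scenario above still favours dupilumab.

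Nor is TCI rescue lost entirely: the additional time-to-event endpoint in 4.5.2 picks it up through Table 5. But that endpoint pools rescue with antidepressants, gabapentin, phototherapy, antihistamines and other items, so it does not isolate rescue, and it too has no stated risk set or censoring.

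It can also be said that the phrase in 4.5.2 is loose wording for all participants, as in ordinary Kaplan-Meier practice. That is plausible, and a clarification would settle it; the censoring rule would still be missing.

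Two stronger readings of Appendix 3 should be resisted. It does not define a conflicting risk set; it is silent. Nor does it say that the rescue analysis runs to Week 36; that is an inference from the concomitant-medication window. A medication-use summary may properly cover longer than an efficacy endpoint, provided its end is stated.

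Finally, rescue counts would not equal primary non-responder counts even after repair. Primary non-response is judged at Week 12 and also includes missing data and prohibited medications.

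**Conclusion.** The concern holds in limited form. The TCS-only list against the TCS-and-TCI definition is a plain mismatch in the text. The Kaplan-Meier risk set is ambiguous, its literal reading is uninformative, and censoring and a between-arm estimate are absent. As written, the plan supports a description of TCS rescue, which is less than the objective claims.

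The size cannot be fixed from the documents. Under the assumed 30% versus 15%, the drug list alone takes the difference from 15 to between 13.5 and 9 points for TCI-only shares of 10% to 40%, and the unstated denominator rule moves the arms between 26% versus 13% and 34% versus 17%. Only the 100% result under the literal reading needs no assumption about rates. Nothing here touches the primary or key secondary conclusions, but the repair is cheap and worth making.

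**What to change.** In SAP 4.5.2, before database lock:

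- **Event.** First use of any Table 5 rescue medication (TCS or TCI), adjudicated as for the responder analyses, from Day 1 through Week 24. Adjudication matters because stable background TCI is permitted. Keep TCS only as a sub-row, and record the change from the protocol-listed endpoint.
- **Risk set and censoring.** All ITT participants, with event-free participants censored at Day 172 or at study exit if earlier.
- **Estimate.** Week 24 cumulative incidence per arm, with the difference and its 95% CI.
- **Companion endpoints.** Apply the same approach to systemic immunosuppressant use. For skin-infection TEAEs, put all safety-population participants at risk, in line with SAP 4.7.
- **Appendix 3.** State where follow-up ends for the rescue summary, and show rescue after Week 24 separately.

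The cost is a documented change to an exploratory endpoint and slightly more analysis work. Event counts may be a little higher. No new data are needed, since rescue drug, dosage and dates are already recorded. The interval may be too wide to demonstrate a reduction, and the report should say so.
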